6. BASELINE, EXPOSURE, AND DISPOSITION

[Appendix A](#) provides a list of planned tables, figures, and listings. Sample data displays are included in a separate document.

6.1. Demographics, Baseline Characteristics, and Disease History

6.1.1. Demographics and Baseline Characteristics

The following demographics and baseline characteristics will be summarized for the FAS population in the DBVC period: age, sex, race, ethnicity, weight, height, and BMI.

6.1.2. Baseline Disease Characteristics

The following baseline disease characteristics will be summarized for the FAS population in the DBVC period:

- Time since first onset of AD
- Prior history of asthma (no/yes)
- Prior allergies (no/yes) and type of allergy
- History of contact dermatitis (no/yes)
- Common complications of AD
- Prior treatments for AD
- Time since onset of current flare of AD
- Prior therapy for AD given in the past 30 days (no/yes)
- Total % BSA involvement in current AD episode
- Total % BSA involving face and/or neck in the current episode
- Facial and/or neck involvement during the past episodes/flare (no/yes)
- Number of AD episodes/flare over the last 12 months
- Average duration of episodes/flare
- IGA score (2/3) at screening
- Baseline IGA score (2/3)
- Baseline facial and/or neck IGA (2/3)
- Baseline EASI score
- Baseline face and/or neck EASI score
- Baseline Itch NRS score

6.1.3. Disease History

Not applicable.

6.1.4. Medical History

For participants in the FAS, medical history will be summarized by assigned treatment group. This summary will include the number and percentage of participants with medical history event for each body system/organ class as documented on the eCRF.

6.2. Disposition of Participant

The number and percentage of participants who were randomized, who were treated, who completed the period, who discontinued study treatment with a primary reason for discontinuation, and who withdrew from the study with a primary reason for withdrawal will be summarized for the FAS population in the DBVC period.

The number and percentage of participants who were treated, who completed the period, who discontinued study treatment with a primary reason for discontinuation, and who withdrew from the study with a primary reason for withdrawal will be summarized for the OL-evaluable population in the OL period.

6.3. Protocol Deviations

Protocol deviations recorded on the eCRF will be summarized and listed for the FAS and OL-evaluable populations.

6.4. Exposure

For participants in the FAS and OL-evaluable population, descriptive statistics will be provided. That is, by treatment group for duration of treatment, average daily weight of study drug, and total weight of study drug. Duration of treatment with ruxolitinib cream or vehicle cream is defined as the number of days from Day 1 to the last record of ruxolitinib cream or vehicle cream application in the specific period.

6.5. Study Drug Compliance

For participants in the FAS population, the overall compliance (%) for the application of ruxolitinib cream or vehicle cream during the DBVC period will be calculated as follows:

$$\text{Overall application compliance (\%)} = 100 \times [\text{total number of nonmissing applications}] / [\text{total number of intended applications}],$$

where the total number of nonmissing applications is the total number of applications that the participant actually applied during the study and the total number of intended applications is the number of planned applications minus the number of interrupted applications.

6.6. Prior and Concomitant Medication

Prior medications and concomitant medications will be coded using the WHO Drug Dictionary. The number and percentage of participants in the FAS population during the DBVC period will be summarized by WHO drug class and WHO drug term for each prior and concomitant medication.

For participants in the OL period, only concomitant medications will be summarized. Prior medications for AD will be summarized by treatment group, as well as listed for the FAS population.

7. EFFICACY

[Appendix A](#) provides a list of planned tables, figures, and listings. Sample data displays are included in a separate document.

7.1. General Considerations

For all continuous variables, both the actual value and change and/or percentage change from baseline (if available) will be analyzed.

All by-visit analyses will include the follow-up period, if the data are available.

7.2. Efficacy Hypothesis

Not applicable.

7.3. Analysis of the Primary Efficacy Parameters

Digital photographs will be used to evaluate clinician-reported outcome assessments (eg, EASI, [REDACTED] and BSA).

7.3.1. Primary Efficacy Measure

7.3.1.1. Eczema Area and Severity Index Score

Atopic dermatitis will be assessed using the EASI scoring system, which is a validated scoring system that grades the physical signs of AD to provide a measure of AD severity (ranging from 0 to 72). The EASI scoring system examines 4 regions of the body (head/neck, upper limbs, trunk, and lower limbs) and weights them. Each of the 4 body regions is assessed separately for erythema (E), induration/papulation/edema (I), excoriations (Ex), and lichenification (L) for an average degree of severity of each sign in each region.

The disease severity strata for the EASI are as follows: 0 = clear; 0.1 to 1.0 = almost clear; 1.1 to 7.0 = mild; 7.1 to 21.0 = moderate; 21.1 to 50.0 = severe; 50.1 to 72.0 = very severe. Specifically for head and neck region, EASI score ranges from 0 to 7.2.

The categorical variable EASI75 of the head and neck region will be equal to 1, if the percentage improvement from baseline of the EASI score is $\geq 75\%$ or greater and will be equal to 0 for percentage improvement of less than 75% for the head and neck region.

Additionally, the categorical variable EASI75 for the entire body (ie, overall) will be equal to 1 if the percentage improvement from baseline of the EASI score is $\geq 75\%$ or greater, and equal to 0 for percentage improvement of less than 75% for the entire body.

7.3.2. Primary Efficacy Analyses

The primary endpoint is the proportion of participants who achieve EASI75 of the head and neck region at Week 4. The primary analysis will be based on the FAS population in the DBVC period. The primary alternative hypothesis (superiority of ruxolitinib 1.5% cream BID compared with vehicle cream BID) will be tested at a 2-sided $\alpha = 0.05$ level using the CMH test stratified by the stratification factor (ie, the participant's face and/or neck IGA score at screening).

Odds ratio in response rates (ruxolitinib cream vs vehicle) at Week 4 will be computed and provided, as well as the p-values. The difference in proportion of participants who achieve an EASI75 score of the head and neck region (ruxolitinib cream vs vehicle) at Week 4 will also be computed. The 95% CI for the difference will be computed based on a large-sample normal approximation with continuity correction. The p-value and stratum-adjusted EASI75 response rate difference with 95% CI will be provided.

All nonresponders during the DBVC period, as well as all participants who discontinue study treatment at any time before Week 4, or withdraw from the study for any reason, will be defined as nonresponders for the NRI analysis.

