10.3. Level of Significance

A hypothesis test will be conducted for the primary analysis at the 2-sided alpha = 0.05 level. In addition, 95% CI will be reported, if applicable.

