10.4. Statistical Analyses

10.4.1. Primary Analysis

The primary endpoint of this study is the proportion of participants who achieve an EASI75 of the head and neck region at Week 4. The primary analysis will be based on the FAS population. The primary alternative hypothesis (superiority of ruxolitinib 1.5% BID compared with vehicle) will be tested using a CMH test stratified by the stratification factor (screening face and/or neck IGA score). Odds ratio in response rates (ruxolitinib cream vs vehicle) at Week 4 will also be computed, and p-values will be provided. The difference in proportion of participants who achieve an EASI75 score of the head and neck region (ruxolitinib cream vs vehicle) at Week 4 will also be computed.

All nonresponders in the DB treatment period, as well as all participants who discontinue study treatment at any time before the timepoint of interest, or withdraw from the study for any reason, will be defined as nonresponders for the nonresponder imputation analysis.

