Rationale for change: Study will be conducted through televisits and mobile nurse home visits. Suitable living environments (eg, internet connect) are important for study conduct.

14. Section 5.4, Screen Failures

Description of change: Added that participants that were terminated before dose administration could be rescreened upon sponsor approval.

Rationale for change: Due to DCT model, the baseline visit is separate from randomization. A participant may be terminated from the study after randomization but before baseline visit/dose administration due to various reasons. Upon sponsor approval, a participant can be rescreened.

15. Section 6.1, Study Treatments Administered; Section 6.5.2, Criteria for Permanent Discontinuation of Study Drug; Section 7.1.1, Reasons for Discontinuation

Description of change: Updated follow-up action to discontinue study treatment when total BSA to be treated exceeds 20%.

Rationale for change: To be consistent with other ruxolitinib cream AD protocols.

16. Section 6.3, Measures to Minimize Bias: Randomization and Blinding

Description of change: Clarified that stratified by screening face and/or neck IGA score

Rationale for change: In the DCT model for this study, only screening IGA is available at randomization. Participants are stratified based on screening IGA score.

17. Section 10.2, Population for Analysis (Table 8: Population Analysis); Section 10.4.1, Primary Analysis

Description of change: The FAS population replaced both the ITT and safety populations.

Rationale for change: For the DCT model for this study, randomization occurs in the screening period and not on Day 1/baseline; therefore, using ITT may include randomized but participants who are terminated from the study early (eg, due to not meeting disease activity criteria at baseline or other reasons) without any baseline values for analysis. Therefore, change from baseline analysis with ITT may not be feasible. The FAS will allow for a meaningful definition of change from baseline in the endpoints.

18. Section 10.4.1, Primary Analysis

Description of change: Change primary analysis from logistic regression to CMH analysis.

Rationale for change: To better characterize the effect size of the efficacy endpoints.

19. Incorporation of administrative changes.

Other regulatory guidance and administrative changes have been incorporated throughout the Protocol and are noted in the redline version of the amendment.

Amendment 1 (28 JUL 2021)

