3.1. Randomization

In the DBVC period, the Interactive Response Technology system will assign approximately 75 participants in a 2:1 ratio to ruxolitinib 1.5% cream BID and vehicle cream BID, respectively. Additionally, participants will be stratified by face and/or neck IGA score (2 or 3) at screening. Participants with a face and/or neck IGA score of 2 at screening will constitute approximately 25% of the overall study population.

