3.3. Sample Size Considerations

Approximately 75 participants will be randomized 2:1 (ie, ruxolitinib 1.5% cream BID to vehicle cream BID, respectively). The sample size calculation is based on the Fisher's exact test for the primary efficacy endpoint. Based on the results from the 2 pivotal studies, INCB 18424-303 and -304, the response rate of EASI75 at Week 4 on the head and neck is assumed to be 55% for the active arm of ruxolitinib 1.5% cream BID versus 15% for vehicle cream BID. Using a 2-sided alpha of 0.05, the sample size will have a > 90% power to detect a difference between the ruxolitinib 1.5% cream BID versus vehicle cream BID. In addition, to provide adequate power for efficacy variables, the sample size is determined to provide a large database for safety evaluation.

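### SAP 7.3.2 leaves the stratum-adjusted confidence interval for the primary EASI75 difference undefined, and the one interval method it names is conservative at 50 versus 25

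*SAP*

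**What the plan says.** SAP 7.3.2 tests the primary endpoint with a CMH test stratified by screening face and/or neck IGA. It also asks for an odds ratio, p-values and the difference in response proportions. For the difference it says: "The 95% CI for the difference will be computed based on a large-sample normal approximation with continuity correction". The next sentence reads: "The p-value and stratum-adjusted EASI75 response rate difference with 95% CI will be provided".

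Nothing else in the documents defines the adjusted interval:

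- Protocol 10.4.1 requires only that the difference be computed.
- Protocol 10.3 says only: "In addition, 95% CI will be reported, if applicable".
- SAP 7.3.4 plans no sensitivity or supportive analysis of the primary endpoint.

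On the strata, SAP 3.1 says: "Participants with a face and/or neck IGA score of 2 at screening will constitute approximately 25% of the overall study population".

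**The concern.** The two sentences may describe one interval or two. If they describe two, the adjusted one has no stated method. If they describe one, the stratum weights, the variance estimator and the form of the correction are still missing. A single correction for the whole table and a correction inside each stratum are different intervals. The programmer would have to settle these points after the SAP is final.

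Separately, a continuity-corrected Wald interval is a doubtful choice with 25 participants on vehicle.

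The superiority decision is not at stake. The interval around the effect is. Protocol Appendix B gives this reason for replacing logistic regression with the CMH analysis: "To better characterize the effect size of the efficacy endpoints". The interval is a main part of that characterisation. It can also disagree with the CMH p-value reported beside it.

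**Working it through.** **1. The plan's own figure.** SAP 3.3 gives about 75 participants at 2:1 (so 50 and 25), 55% versus 15%, two-sided alpha 0.05 and Fisher's exact test. Exact enumeration gives 93.8% power, which agrees with the stated figure of more than 90%.

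**2. The named interval at 50 versus 25.** The interval is d ± (1.96·SE + c).

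- SE at the planning rates: √(0.55·0.45/50 + 0.15·0.85/25) = 0.1002, so 1.96·SE = 0.196.
- Correction: c = 0.5·(1/50 + 1/25) = 0.030.
- Half-width: 0.196 + 0.030 = 0.226, which is 15% more than without the correction.

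Enumerating all 51 × 26 = 1,326 tables gives 96.7% coverage and mean limits of 17.75 to 62.25 points (width 44.5). The lower limit lies above the true difference in 2.4% of trials and the upper limit lies below it in 0.85%, against 2.5% nominal on each side. Without the correction, coverage is 93.2%. Newcombe's interval covers 94.8% with a width of 38.4. Over active rates of 40–70% and vehicle rates of 5–29%, the corrected interval covers 96.1% to 97.5%.

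**3. The stratum-adjusted interval.** The strata are an assumption taken from the approximate 25% share: IGA 2 with 12/6 and IGA 3 with 38/19, and the same response rates in both.

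- MH weights are proportional to n₁n₂/N: 12·6/18 = 4 and 38·19/57 = 12.67, so 0.24 and 0.76.
- One overall correction: 0.030, as above.
- Correction within strata: 0.24·0.5·(1/12 + 1/6) + 0.76·0.5·(1/38 + 1/19) = 0.030 + 0.030 = 0.060.

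The table is an exact enumeration of 13·7·39·20 = 70,980 tables; the first row's coverage, width and limits come from step 2. The last two columns give how often the interval and an uncorrected CMH test disagree about zero, in either direction. The 55% versus 25% case is an illustration; the plan gives only 55% versus 15%.

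| Interval | Coverage | Mean width | Mean limits | Disagree, 55/15 | Disagree, 55/25 |
|---|---|---|---|---|---|
| Named crude interval | 96.7% | 44.5 | 17.75 to 62.25 | 0.9% | 3.2% |
| MH, no correction | 93.1% | 37.9 | 21.05 to 58.95 | 1.7% | 5.0% |
| MH, one overall correction | 96.6% | 43.9 | 18.05 to 61.95 | 0.8% | 2.5% |
| MH, correction within strata | 98.3% | 49.9 | 15.05 to 64.95 | 4.4% | 11.9% |
| Stratified Miettinen-Nurminen, MH weights | 94.9% | 39.1 | 17.8 to 56.9 | 0% | 0% |

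Strata of 13/6 and 37/19 change the 55/15 coverages, widths and limits by at most 0.1 point.

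**4. One data set.** Take 7/12 versus 1/6 in IGA 2 and 21/38 versus 3/19 in IGA 3. The adjusted difference is 0.24·0.4167 + 0.76·0.3947 = 0.40, with SE 0.1015. The three readings give 20.1 to 59.9, 17.1 to 62.9 and 14.1 to 65.9 points.

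**5. Why the score interval agrees with CMH.** In the same data set:

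- CMH numerator: (7 − 12·8/18) + (21 − 38·24/57) = 1.667 + 5 = 6.667.
- CMH variance: 12·6·8·10/(18²·17) + 38·19·24·33/(57²·56) = 1.046 + 3.143 = 4.189.
- CMH statistic: 6.667²/4.189 = 10.61.
- Score variance at difference zero, with factor N/(N−1): 0.24²·(8/18)(10/18)(1/12 + 1/6)(18/17) + 0.76²·(24/57)(33/57)(1/38 + 1/19)(57/56) = 0.00376 + 0.01131 = 0.01508.
- Score statistic: 0.40²/0.01508 = 10.61.

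The same identity held in all 70,980 tables.

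**The case against.** The strongest reply is that this is a clarification. The limit that supports superiority is already right: the named interval's mean lower limit is 17.75 against 17.8 for the score interval, and its lower-side error is 2.4%. Erring on the wide side in a phase 2 trial does little harm. That is correct, and it limits the size of the point.

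Other parts also stand:

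- The correction explains only 3.0 of the roughly 5 points at the upper limit (59.25 to 62.25). The remaining 2.35 (59.25 − 56.9) is the difference between a Wald and a score interval.
- Nothing in the text suggests correcting within strata, so the 98.3% and 11.9% figures rest on the least likely reading. Without it, the widths still run from 37.9 to 43.9 points, on opposite sides of 95% coverage.
- Newcombe's interval has its own imbalance. The crude version misses 1.47% on the lower side and 3.78% on the upper side at 55% versus 15%.
- The named method may be meant to carry over to the adjusted interval. If so, the method is not wholly open, but the weights, the variance and the form of the correction are.

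The table shells are in a separate document that was not available. They may settle some of this, but the definition of the primary interval belongs in the SAP. None of these points supplies the missing definition.

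**Conclusion.** The concern holds on both counts. The adjusted interval is promised without a definition, and the admissible readings give mean widths from 37.9 to 49.9 points from the same data. The named crude interval covers 96.7%. It is about 14% wider than a near-nominal stratified score interval (44.5/39.1 = 1.14), and its upper limit is about 5 points too high (62.25 against 56.9).

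The effect is confined to the reported precision of the primary difference and its agreement with the CMH p-value. The CMH decision, type I error and power do not change. This should be corrected, but it does not threaten the trial's conclusion.

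The figures assume exactly 50 and 25 participants, strata of 12/6 and 38/19 with equal rates, and a CMH test without continuity correction, on which the SAP is silent. The FAS may be smaller than 75, which would enlarge the correction.

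**What to change.** Replace the two CI sentences in SAP 7.3.2 with one definition:

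- The estimate is the MH-weighted risk difference, stratified by screening face and/or neck IGA (2 or 3).
- The 95% CI is the stratified Miettinen-Nurminen score interval with the same weights, variance factor N/(N−1) within stratum, and no continuity correction.
- This is the only CI for the difference reported with the CMH test, and the CMH test is uncorrected.

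A stratified Newcombe interval is an acceptable closed-form alternative. It would still disagree with CMH in about 0.5% of trials at 55% versus 15% and about 3% at 55% versus 25%, mainly by excluding zero when CMH is not significant.

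The cost is a SAP amendment, since the SAP is already issued, plus programming and validation of a short iterative routine. It needs no patients, no data and no Protocol amendment, because Protocol 10.3 and 10.4.1 name no CI method. The trade-off is coverage of about 95% in place of a conservative interval.

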7.3. Lost to Follow-Up

After consent is signed, a participant will be considered lost to follow-up if he/she is not able to attend for one scheduled visit and is unable to be contacted by the study site to reschedule, despite all efforts from site staff to contact.

The following actions must be taken if a participant fails to be available for a required telemedicine and in-home healthcare worker study visit:

- The site must attempt to contact the participant and reschedule the missed visit as soon as possible and counsel the participant on the importance of maintaining the assigned visit schedule and ascertain whether or not the participant wishes to and/or should continue in the study.
- Before a participant is deemed lost to follow-up, the investigator or designee must make every effort to regain contact with the participant. These contact attempts should be documented in the participant's medical record.
- Should the participant continue to be unreachable, they will be considered to be lost to follow-up and have withdrawn from the study.

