8.9. End of Treatment and/or Early Termination

When the participant permanently discontinues study drug, whether the participant is terminating the study early or the participant has completed the study, the EOT visit (at Week 4 EOT1 for end of DB VC period and at Week 8 EOT2 for end of OL period) should be conducted. If the EOT visit coincides with a regular study visit, the EOT evaluations will supersede those of that scheduled visit, and the data should be entered in the EOT visit in the eCRF. If a participant withdraws from the study before or on Week 4, EOT1 should be conducted. If a participant withdraws from the study after Week 4 and before or on Week 8, EOT2 should be conducted. The participant should be encouraged to complete the follow-up visit.

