2.1 EASI			
2.1.1	Summary and Analysis of Participants Who Achieved EASI75 of the Head and Neck Region During the Treatment Period	FAS	
2.1.3	Summary and Analysis of Participants Who Achieved an Overall EASI75 During the Treatment Period	FAS	

Exposure and Safety			

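### The Week 4 nonresponder rule puts a time limit on stopping treatment but none on study withdrawal: a minor error in the stated rule, fixed by one clause

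*SAP*

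**What the plan says.** SAP 7.3.2 fixes the endpoint: "The primary endpoint is the proportion of participants who achieve EASI75 of the head and neck region at Week 4". It also fixes the scope: "The primary analysis will be based on the FAS population in the DBVC period". Its nonresponder rule then covers nonresponders during the double-blind vehicle-controlled (DBVC) period and all participants who "discontinue study treatment at any time before Week 4, or withdraw from the study for any reason, will be defined as nonresponders".

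Protocol 10.4.1 is built the same way. It makes nonresponders of participants who "discontinue study treatment at any time before the timepoint of interest, or withdraw from the study for any reason".

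SAP 4.1.4 gives a general rule for response endpoints. Participants with missing postbaseline values count as nonresponders, and withdrawal is not mentioned.

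Both documents provide for withdrawal after Week 4:
- Protocol 8.9: "If a participant withdraws from the study after Week 4 and before or on Week 8, EOT2 should be conducted".
- SAP 6.2: participants "who withdrew from the study with a primary reason for withdrawal will be summarized for the OL-evaluable population in the OL period".
- Protocol 7.3, on participants who remain unreachable: "they will be considered to be lost to follow-up and have withdrawn from the study". Under Protocol 4.2, completing the study includes the safety follow-up visit, so this can happen after treatment has ended.

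**The concern.** The rule has two triggers. Stopping treatment counts only if it happens before Week 4. Withdrawing from the study counts whenever it happens. A participant can therefore have a Week 4 EASI score that meets EASI75, enter the open-label period, withdraw at Week 6 and, under the rule as worded, be counted as a Week 4 nonresponder.

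That would let events from a period in which every continuing participant is assigned ruxolitinib cream, or from follow-up, overwrite an outcome already observed under blinded treatment. The endpoint affected is the only one with a planned hypothesis test (Protocol 10.3, SAP 3.2); SAP 7.4 makes the secondary endpoints descriptive. SAP 7.3.4 plans no sensitivity or supportive analysis of the primary endpoint, so no planned output would show that the literal rule had been applied.

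**Working it through.** **1. The wording**

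| Place | Limit on stopping treatment | Limit on withdrawal |
|---|---|---|
| SAP 7.3.2 | before Week 4 | none |
| Protocol 10.4.1 | before the timepoint of interest | none |
| SAP 4.1.4 | not mentioned | not mentioned; missing values decide |

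In SAP 7.3.2 the reference to the DBVC period at the start of the rule qualifies the nonresponders. It does not grammatically reach the withdrawal clause. The literal gap is real, and the protocol does not close it.

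**2. The plan's own power figure**

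Inputs (Protocol 10.1, SAP 3.3): 75 participants at 2:1, so 75 × 2/3 = 50 active and 75 × 1/3 = 25 vehicle; response 55% v 15%; two-sided alpha 0.05; Fisher exact test. Exact enumeration gives 93.8% power, which agrees with the stated figure of more than 90%.

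The planned stratified CMH test gives 94.7%. This assumes no continuity correction, strata of 12 + 6 (IGA 2) and 38 + 19 (IGA 3), and equal response rates across strata. Limiting withdrawal to before Week 4 changes none of these figures.

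**3. Effect of one recoded participant under the literal reading**

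- Active responder recoded: 1/50 = 2 points off the crude difference.
- Vehicle responder recoded: 1/25 = 4 points on to the crude difference.

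The two arms push in opposite directions, so the net direction is not known in advance.

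**4. Illustration under assumed withdrawal**

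The documents give no withdrawal rate after Week 4, so the share w of Week 4 responders who later withdraw is an assumption. If w is equal in both arms, the difference is 0.55(1 − w) − 0.15(1 − w) = 0.40(1 − w).

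| w | Rates | Difference | Expected recoded, active / vehicle | CMH power |
|---|---|---|---|---|
| 0 | 55.0% v 15.0% | 40 points | 0 / 0 | 94.7% |
| 5% | 52.3% v 14.3% | 38 points | 1.4 / 0.2 | about 93% |
| 10% | 49.5% v 13.5% | 36 points | 2.75 / 0.4 | 90.5% |
| 20% | 44.0% v 12.0% | 32 points | 5.5 / 0.75 | 84.4% |

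Unequal shares move the result either way. With 20% in the active arm only, the difference is 44% − 15% = 29 points and CMH power is about 74%. With 20% in the vehicle arm only, it is 55% − 12% = 43 points and about 98%.

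Tipping point from a result near the plan, 28/50 v 4/25 (56% − 16% = 40 points, CMH p = 0.0011), with no vehicle responder recoded:
- 8 active responders recoded: 20/50 v 4/25, 24 points, p = 0.038.
- 9 recoded: 19/50 v 4/25, 22 points, p = 0.055.

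Losing significance therefore needs 9 of 28 active responders (32%) to withdraw after Week 4, and none in the vehicle arm.

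**The case against.** The strongest reply is that context settles the meaning. The endpoint is response at Week 4, the primary analysis is confined to the DBVC period, and SAP 6.2 reports withdrawals separately by period. SAP 4.1.4 makes nonresponse depend on missing values, which gives no reason to recode an observed Week 4 response. Using later events to overwrite a double-blind result would be an odd thing to intend.

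All of this stands as evidence of intent, and it is why the point is minor. It does not correct the sentence. SAP 7.3.2 is the specific rule for the primary endpoint, and SAP 4.1.4 neither mentions withdrawal nor says which of the two rules governs.

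Three stronger readings are tempting, and the documents support none of them:
- *The analysis will be run with open-label withdrawals counted as Week 4 failures.* Nothing says so, and the context points the other way.
- *The title of SAP Appendix A Table 2.1.1, "Summary and Analysis of Participants Who Achieved EASI75 of the Head and Neck Region During the Treatment Period", shows that the rule spans both periods.* Head-and-neck EASI75 is an endpoint at Weeks 2, 4 and 8, which is enough to explain a table covering the whole treatment period. The title says nothing about how Week 4 nonresponse is derived.
- *The trial's conclusion is at risk.* This would need heavy and one-sided withdrawal, for which the documents give no basis.

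**Conclusion.** The nonresponder rule is wrong as worded in SAP 7.3.2 and Protocol 10.4.1, because study withdrawal carries no time limit. Withdrawal before the Week 4 assessment is almost certainly meant. The severity is minor: no stated figure is wrong, and what remains is a small, avoidable risk that the primary endpoint is derived as written.

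The shifts of 2 and 4 points per participant rest only on the 50 v 25 split. The power and tipping-point figures rest in addition on assumed withdrawal shares, equal response rates across strata and a literal reading that is probably not intended, so they are illustrative. At the planned effect the estimate could move by a few points, but the conclusion is unlikely to change.

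**What to change.** In SAP 7.3.2, replace the rule with: *Participants who discontinue study treatment or withdraw from the study before the Week 4 assessment, or whose Week 4 EASI is missing, are nonresponders at Week 4; events after the Week 4 assessment do not change Week 4 response.*

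Align SAP 4.1.4 by saying that the missing value meant is the one at the visit being analysed. At the next protocol amendment, apply the timepoint limit in Protocol 10.4.1 to withdrawal as well as to stopping treatment.

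Do not add a new rule tying the Week 4 assessment to the ± 3-day visit window. Combined with the missing-value clause, it could turn a completed visit that fell outside the window into nonresponse, which is a separate decision with its own effect on the endpoint.

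The cost is one clause in SAP 7.3.2 and a matching edit in SAP 4.1.4. No new data are needed, and the sample size and power do not change. The protocol edit can wait.
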